Implementation Fidelity. An intervention fidelity rating tool¹⁴ was used to assess the extent to which the therapist promoted the components of SDT (autonomy, relatedness, competence, and general impression). Four items were rated on a 0-4 Likert scale, and then summed to produce a total score range of 0-16, with the higher scores indicating higher intervention fidelity. A licensed occupational therapist, who was not involved in the intervention delivery or the administration of the other assessments, was instructed on how to use the measure. The assessor viewed and rated 12 sessions (one from each participant), that had been previously recorded via Zoom. In addition to the ratings, the assessor identified quotes from the therapist and participant that illustrated promotion of autonomy, relatedness, and competence.

Efficacy outcome measures.

Efficacy of the intervention was assessed in regards to effect estimates comparing pre and post intervention for physical activity, self-efficacy, motivation and self-performance of performance and satisfaction on goals. In addition to measures of feasibility and acceptability, there were two primary efficacy outcomes: 1) change from baseline in moderate vigorous physical activity using Actigraph, and 2) change from baseline in the relative autonomy index (RAI) of the behavioral regulation in exercise questionnaire (BREQ-2). Table 2 includes a summary of the efficacy outcome measures.

Table 2. Efficacy Outcome Measures

| Effect Estimate Domain | Outcome Measures | Variable Name | When |
|---|---|---------------|--|
| Physical Activity | Brunel Lifestyle Physical Activity Questionnaire ²¹ | Brunel-PAQ | 2x, Baseline and follow-up |
| Physical Activity | Wearable activity monitor | ActiGraph | 2x, Worn 7 consecutive days pre and post intervention |
| Self-efficacy | The Exercise Self-Efficacy Scale ²² | Norman-SES | 2x, Baseline and follow-up |
| Motivation | The Behavioral Regulation In Exercise Questionnaire ²³ | BREQ-2 | 2x, Baseline and follow-up |
| Self-perception of Performance & Satisfaction | Modified Canadian Occupational Performance Measure ²⁴ | mCOPM | 2x, First and last session |

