Motivation. The Behavioral Regulation in Exercise Questionnaire (BREQ-2) measures the stages of self-determination continuum with respect to motivation to exercise.²³ It is a 19-item questionnaire, with a 5 point Likert scale from 0 “not true for me” to 4 “very true for me” for statements regarding PA engagement. For example, “I don't see why I should have to exercise” (amotivation), “I exercise because other people say I should” (extrinsic), “I feel guilty when I don't exercise” (introjected), “I value the benefits of exercise” (identified) and “I exercise because it is fun” (intrinsic). Acceptable internal consistency was previously demonstrated for the 5 subcategories: amotivation (items 5, 9, 12 & 19), external regulation $\alpha = .81$ (items 1, 6, 11 & 16), introjected regulation $\alpha = .79$ (items 2, 7 & 13), identified regulation $\alpha = .78$ (items 3, 8, 14 & 17), and intrinsic motivation $\alpha = .93$ (items 4, 10, 15 & 18).³⁰ A composite score of intrinsic motivation and identified regulation subscales represented autonomous motivation ($\alpha = .90$).³⁰ A composite score of introjected regulation and external regulation represented controlled motivation ($\alpha = .78$).³⁰ The BREQ-2 was scored by calculating the mean scores for each set of items per domain as indicated by its scoring key.

Self-perception of Performance & Satisfaction. The Canadian Occupational Performance Measure (COPM)²⁴ is a tool used to detect change in participant's self-perception of occupational performance, in regards to performance and satisfaction, over time using two 10-point ordinal scales, with 10 being the best score. The COPM was designed to enable personalized health care and identify issues of personal importance to the client. The COPM is a tool for initiating conversation about performance issues in everyday living, which provides the basis for setting intervention goals. More specifically, the COPM helps the therapist to: (1)

identify problem areas in occupational performance; (2) provide a rating of the client's priorities in occupational performance; (3) evaluate performance and satisfaction relative to those problem areas; (4) provide the basis for goal setting; and (5) measure changes in client's perception of his/her occupational performance over the course of the intervention.

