Correlation coefficients were calculated to determine the relationship between: post-pretest change scores of planned PA and self-efficacy; baseline self-efficacy scores and follow-up planned-PA times; and post-pretest change scores of planned PA and unplanned PA and BREQ-2 measures of amotivation, external regulation, introjected regulation, identified regulation, and intrinsic regulation.

References

9. Michie S, van Stralen MM, West R. The behaviour change wheel: A new method for characterising and designing behaviour change interventions. *Implement Sci*. 2011;6(1):42.
12. Kandiah N, Zhang A, Cenina AR, Au WL, Nadkarni N, Tan LC. Montreal Cognitive

- Assessment for the screening and prediction of cognitive decline in early Parkinson's disease. *Parkinsonism Relat Disord.* 2014;20(11):1145-1148.
13. Reed GR. *The Transtheoretical Model and Exercise Behavior: A Comparison of Five Staging Methods.*; 1993.

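### Does the plan leave its primary motivation outcome, change in the BREQ-2 relative autonomy index, without a result?

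*Combined protocol and SAP*

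**What the plan says.** In Efficacy outcome measures the protocol states that "there were two primary efficacy outcomes": change in ActiGraph-measured moderate-to-vigorous activity, and "change from baseline in the relative autonomy index (RAI) of the behavioral regulation in exercise questionnaire (BREQ-2"). That sentence is the only mention of the RAI. Table 2 lists the instrument simply as BREQ-2, at baseline and follow-up.

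The Motivation paragraph describes the instrument: "It is a 19-item questionnaire, with a 5 point Likert scale from 0" to 4. It assigns the items to five subscales, and the scoring sentence reads: "The BREQ-2 was scored by calculating the mean scores for each set of items per domain as indicated by its scoring key". Two further sentences describe composites: "A composite score of intrinsic motivation and identified regulation subscales represented autonomous motivation" and "A composite score of introjected regulation and external regulation represented controlled motivation". Each carries a Cronbach's alpha cited to an earlier validation study.

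The Statistical Analysis applies descriptive statistics, the mean baseline-to-follow-up difference with a 95% confidence interval, and Cohen's d to every efficacy measure, including motivation measured by the BREQ-2. It does not say which BREQ-2 score. The correlation paragraph relates changes in planned and unplanned activity to "BREQ-2 measures of amotivation, external regulation, introjected regulation, identified regulation, and intrinsic regulation".

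**The concern.** A primary outcome should be traceable from its name, through its derivation, to the analysis that reports it. Here the trail appears to break twice. The scoring text gives subscale means and two composites, none of them called the RAI, and neither composite uses the amotivation items. The analysis text names only the questionnaire, or else its subscales.

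If that were the whole plan, a named primary outcome could go unreported, and one of several other scores from the same questionnaire could take its place once the data were known. The missing formula also matters numerically: an index built from subscale means can change size, and even sign, with the weights used.

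**Working it through.** **1. Item map.** The only figure in the plan that can be checked on this point is the item count. From the Motivation paragraph: amotivation 4, external 4, introjected 3, identified 4, intrinsic 4.

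4 + 4 + 3 + 4 + 4 = 19

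Items 1 to 19 each appear once. The plan's figure is reproduced, and the scoring sentence gives five subscale means with no item left over.

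**2. The statements side by side.**

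| Place | What it settles | What it leaves open |
|---|---|---|
| Efficacy outcome measures | The primary BREQ-2 score is RAI change | The formula |
| Motivation | Five subscale means, scored by the instrument's key | How they combine into the RAI |
| Statistical Analysis, pre-post | Mean change, 95% CI and Cohen's d for the BREQ-2 | Which BREQ-2 score |
| Statistical Analysis, correlations | Five subscales against activity change | Nothing about the primary comparison |

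Each gap in the pre-post chain except the formula is closed by another row. The score left open in the third row is given in the first. The subscale means in the second row do not compete with the index if it is built from them. The correlations are a separate analysis and do not replace the pre-post change.

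**3. Does the formula matter?** Yes, if the weights were free. Take assumed changes in the subscale means: amotivation −0.4, external 0, introjected +0.5, identified +0.1, intrinsic 0. With weights in that order, all of them assumed:

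- Graded (−3, −2, −1, +2, +3): 1.2 + 0 − 0.5 + 0.2 + 0 = +0.9
- Equal (−1, −1, −1, +1, +1): 0.4 + 0 − 0.5 + 0.1 + 0 = 0.0
- Autonomous mean minus controlled mean: (0.1 + 0)/2 − (0 + 0.5)/2 = −0.2
- Graded without amotivation (0, −2, −1, +1, +2): 0 + 0 − 0.5 + 0.1 + 0 = −0.4

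The spread shows why one fixed definition is needed. It does not show that the analyst may choose: the plan presents the RAI as an index of this questionnaire, and it scores the questionnaire by its key.

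**4. Multiplicity.** Counting five subscales and two composites gives seven scores, and 1 − 0.95^7 = 0.302. This requires seven independent scores. The composites are formed from four of the five subscales, so independence is impossible. With the five subscales alone, still assumed independent, the figure is 1 − 0.95^5 = 0.226.

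A simulation kept the real structure: five subscale changes and two averages of them, normal data, true change zero, n = 12 assumed (the fidelity section refers to 12 sessions, one from each participant). The chance that at least one 95% interval excludes zero was about 26%, 23%, 20% and 16% at subscale correlations of 0, 0.3, 0.5 and 0.7. Results at n = 30 were nearly the same.

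All these figures assume that a claim is made whenever any interval excludes zero. The plan contains no such rule. It sets no alpha, power or success criterion for efficacy, and it describes the aim as effect estimates.

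**The case for a change.** The strongest case for a change is that an estimator needs a defined variable. The plan calls this outcome primary, makes effect estimates a stated aim, and gives the RAI no formula, range or direction. The scoring key is invoked only for subscale means and is not reproduced, so a reader cannot rebuild the RAI from this document. Writing it down would take two sentences and no new data.

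The factual part stands: the formula is absent, and the analysis section does not repeat the outcome's name. It does not follow that the outcome has no planned result. The outcome statement identifies the score and the pre-post paragraph supplies its analysis. The count of seven rival scores is also uncertain. The composite sentences can be read as psychometric background from the cited validation study, and neither composite appears in the Statistical Analysis. Substitution after the data are seen is possible in any study, but here the named primary outcome is what would expose it.

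**Conclusion.** The concern does not call for a change. The gap is one unwritten formula and one outcome name not repeated. An analyst following the outcome statement, the scoring paragraph and the pre-post analysis together would form the index from the five subscale means and report its mean change with a 95% confidence interval and Cohen's d.

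No decision in the plan turns on it. This is an uncontrolled feasibility study whose stated thresholds concern session adherence, retention, activity-log completeness and the acceptability questionnaire total; none uses the RAI. Neither the 30% figure nor the simulated 16% to 26% measures an error rate of this plan, because there is no claim rule to which they could apply.

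The conclusion assumes that the scoring key, or the instrument's established scoring, gives a single definition of the index. The documents do not reproduce the key, so this cannot be confirmed from them. If several definitions were in use, the sign reversals in the illustration would be a real reporting risk, but nothing in the text indicates that.

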The ActiGraph™ GT9X quantitatively measured PA levels (step count, MVPA levels, and sedentary behavior) to assess change before and after the intervention. Actigraphy is a non-invasive way of monitoring human rest/activity cycles and has been used to study PA levels and patterns in PwPD who have mild to moderate severity.^{26–28} The ActiGraph™ GT9X is a reliable assessment of steps for PwPD or altered gait in both clinical and research evaluations.²⁹ The ActiGraph™ is an inertial measurement unit (IMU) which includes an accelerometer, a gyroscope, and magnetometer sensors to capture position and rotation, and wear time sensor. Participants were instructed to wear the ActiGraph™ secured on their hip by an elastic clip-on waist band on their hip for 7 consecutive days prior to receiving the intervention, and again after their last session. In addition, participants were asked to keep a written log, using handouts provided, to record times when the ActiGraph™ was removed and put it back on. Participants were instructed to not wear the device in water, such as when bathing or during water sports.

Self-efficacy. Self-efficacy was measured by the Exercise Self-Efficacy Scale (Norman-SES).²² The Norman-SES is an 18-item test that measures an individual's self-efficacy to participate in exercise when numerous barriers are present, including both social and physical barriers. The measure employs a 5-point Likert scale for confidence, from 1 “not at all confident” to 5 “completely confident”, in the areas of negative affect ($\alpha = .853$), excuse making ($\alpha = .829$), must exercise alone ($\alpha = .869$), inconvenient to exercise ($\alpha = .773$), resistance from others ($\alpha = .853$), and bad weather ($\alpha = .837$). A score less than or equal to 54 indicated low self-efficacy (18 items x Likert score of 3 “neutral”), a score between 54 and 72 (18 items x Likert score of 4 “confident”), and a score between 72 and 90 (18 items x Likert score of 5 “completely confident”) indicates high self-efficacy.

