Percentage of participants who selected Fitbit as their primary PA log was reported. Descriptive statistics were calculated for Fitbit data with regards to total percentage of time worn and daily step counts for the first and last 7 days. Data from the FitBit devices were synced with Fitabase program to provide sync events, wear time, number of steps per day, and moderate-vigorous activity. The data were downloaded into a .csv file for all participants for the duration of their intervention (16 weeks). Aggregate data were then calculated to provide mean and SD for all metrics

Descriptive statistics were calculated for the outcome measures for baseline and follow-up: PA levels (Brunel-PAQ and ActiGraph™), exercise self-efficacy (Norman-SES), motivation to exercise (BREQ-2), and self-perception of performance & satisfaction of goals (mCOPM). The mean difference between the baseline and follow-up was then calculated with a 95% confidence interval (CI). Effect sizes were calculated using Cohen's d ³⁹, with $d = 0.2$ being considered a small effect size, $d = 0.5$ a medium effect size, and $d = 0.8$ a large effect size.

Descriptive statistics were calculated for participants in the different stages of exercise behavior change (URICA-E2) with regards to their changes in exercise self-efficacy (Norman-SES) and planned PA (Brunel-PAQ). Descriptive statistics were also calculated for changes in kinds of PAs enjoyed (Brunel-PAQ) from baseline to follow-up. ActiGraph™ findings were calculated with regards to percentage of time spent in sedentary activity, percentage of time in MVPA, and daily step count.

The accelerometry data were preprocessed as accelerometer data files (AGD files) using ActiLife software (ActiLife v6.13.2; Pensacola, FL, 2016) and then converted to CSV files with 60-second epochs. Participants with less than 4 days (and a minimum of 1 weekend day) of 10 hours per day of wear time were excluded from the results. Based on the results of earlier studies, 60 minutes of consecutive zero counts were classified as non-wear time. Non-wear time was excluded from calculations for each individual.

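### Does the 60-minute zero-count rule for ActiGraph non-wear let short removals distort the activity results?

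*Combined protocol and SAP*

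**What the plan says.** The Physical Activity Levels text under Efficacy outcome measures describes a hip-worn device containing an accelerometer, "a gyroscope, and magnetometer sensors to capture position and rotation, and wear time sensor". It tells participants when to remove it: "Participants were instructed to not wear the device in water, such as when bathing or during water sports". It also says that "participants were asked to keep a written log, using handouts provided, to record times when the" device came off and went back on.

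The Statistical Analysis section then sets out the processing, on 60-second epochs. Wear time is defined by a single criterion, "60 minutes of consecutive zero counts were classified as non-wear time", which the plan attributes to earlier studies. It adds: "Non-wear time was excluded from calculations for each individual". The inclusion rule is that those recording "less than 4 days (and a minimum of 1 weekend day) of 10 hours per day of wear time were excluded from the results". The ActiGraph results are "percentage of time spent in sedentary activity, percentage of time in MVPA, and daily step count".

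No section says that the removal log or the wear sensor was used to set wear time, and none says that they were not. No count cut-points for sedentary time or MVPA are given. Change in MVPA is one of two primary efficacy outcomes.

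**The concern.** The protocol itself creates short removals, since bathing will usually take less than an hour, and the only stated detection rule cannot see a removal of that length with movement on either side. Those minutes would enter the denominator as wear and, having zero counts, would fall in the lowest activity class. The sedentary percentage would be too high and the MVPA percentage too low. A day with less than 10 hours actually worn could pass as valid, which bears on who is in the ActiGraph results.

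The two wear weeks are about 15 weeks apart, with an activity intervention between them, so equal removal patterns cannot be taken for granted. Participants were also asked to record the very information that would settle the matter, so leaving it unused would look like waste.

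**Working it through.** The plan gives no figure to reproduce, so the check has three parts: what the rule does, how large the error is, and whether valid days are affected.

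**1. The rule.** Applied to one-minute records with movement on both sides, removals of 15, 30, 45 and 59 minutes have 0 minutes flagged, and removals of 60 and 90 minutes are flagged in full. A 40-minute removal next to 20 minutes of zero-count stillness forms a 60-minute run and is flagged. The mechanism is therefore as feared, for isolated removals only.

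**2. Size.** From the documents: the 60-minute rule and the 7-day wear period. Assumed, because the documents do not give them: recorded wear 14 h/day, MVPA 20 min/day, true sedentary share *s* of 55% to 75%, and the removal patterns.

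Weekly recorded wear W = 7 × 840 = 5880 min. Removed time left in is r, and true wear is T = W − r. Weekly MVPA is 7 × 20 = 140 min.

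- Sedentary error = (sT + r)/W − s = (1 − s) × r/W
- MVPA error = 140/W − 140/T

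| Removals in one week | r (min) | T (min) | Sedentary error, s = 75% to 55% (points) | MVPA error (points) |
|---|---|---|---|---|
| Three of 45 min | 135 | 5745 | +0.57 to +1.03 | −0.06 |
| 15 min daily | 105 | 5775 | +0.45 to +0.80 | −0.04 |
| 20 min daily | 140 | 5740 | +0.60 to +1.07 | −0.06 |
| 59 min daily (maximum for one isolated removal a day) | 413 | 5467 | +1.76 to +3.16 | −0.18 |

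*Pre-post change, same three 45-minute removals in both weeks.* Let the sedentary share fall from 65% to 63% and MVPA rise from 20 to 30 min/day. The sedentary errors are 0.35 × 135/5880 = 0.80 and 0.37 × 135/5880 = 0.85 points, a net 0.05. The MVPA change is recorded as 70/5880 = 1.19 points against a true 70/5745 = 1.22, an error of 0.03.

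*Removals in one week only* (65% sedentary, 20 min/day MVPA): 0.80 and 0.06 points, in either direction.

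*Stress case.* Take 15 min/day removed at baseline and 59 min/day at follow-up, with no true change, MVPA 30 min/day and a 65% sedentary share. With 840 min true wear, MVPA shifts by 30/899 − 30/855 = −0.17 points; with 600 min, by 30/659 − 30/615 = −0.33 points. Sedentary time shifts by +1.7 and +2.3 points.

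*The opposite error.* The same rule also deletes genuine stillness of 60 minutes or more. If n such minutes are deleted, the recorded sedentary share is (sT + r − n)/(T + r − n), so only r − n matters. The 135 minutes from three 45-minute removals would be offset exactly by 135 minutes of deleted stillness in the week, for example two spells of 67.5 minutes. The sign of the net error is therefore not established.

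**3. Valid days.** At 14 h recorded wear, a 45-minute removal leaves 840 − 45 = 795 min, well above 600. Status changes only for days actually worn 580–599 min (20-minute removal), 555–599 min (45-minute) or 541–599 min (59-minute), because 580 + 20 = 555 + 45 = 541 + 59 = 600. A participant's inclusion changes only if such a day was needed for the 4-day minimum or was the only valid weekend day. The documents do not allow the frequency of this to be estimated.

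**The case for a change.** The best case for acting is that the correction is cheap. The log was already requested, applying it would take a few hours if the logs were returned, and it bears on a primary outcome reported as a percentage, where the denominator counts. The errors do not cancel if removal habits changed, and the stress case shows a spurious MVPA shift of 0.17 to 0.33 points against true levels of 3.57% (30/840) to 5.00% (30/600). In a small sample, one participant passing the valid-day rule wrongly would matter.

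Part of this stands. The plan should have said whether the log was used, and one sentence in the study report would settle it. But the stress case needs nearly an hour off the device every day at follow-up and only a quarter of that at baseline, and nothing in the documents suggests such a pattern.

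The proposed correction also has costs. Log times are self-reported, and unlogged removals stay in. Adding logged removals to the zero-count rule can only subtract wear time, so it leaves wrongly deleted stillness where it is. It could also drop a participant. The Implementation Fidelity text, with 12 rated sessions, one per participant, suggests about 12 people, so losing one would be 1/12, or about 8% of the sample. That could move a mean change by more than 0.03 to 0.06 points.

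Uncaptured exercise in water is a separate limitation. No non-wear rule recovers it.

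**Conclusion.** This is a reporting gap that does not undermine the analysis. Whether any error occurred is unknown: the natural purpose of a removal log is to identify non-wear, and the statement that non-wear was excluded is compatible with its use.

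If the stated rule was applied alone, the MVPA percentage moves by 0.04 to 0.06 points in a week under ordinary assumed removals and by 0.18 with a 59-minute removal every day. The pre-post error is 0.03 points with matched removals and 0.06 with removals in one week only. The sedentary percentage moves more, by about 0.5 to 1 point, but it is not a primary outcome and its error also largely cancels when removals are similar. MVPA minutes and steps on a given day do not change at all.

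No decision turns on these amounts. The ActiGraph results are reported as a mean difference with a 95% confidence interval and Cohen's d, and the adherence and retention criteria do not use them.

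The sizes rest on assumed wear, MVPA, sedentary share and removal patterns, none of which the documents supply. The 60-minute rule can stand as the main definition. Replacing it is a debatable trade-off with no demonstrated gain.
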